7.2 PARTICIPANT DISCONTINUATION OR WITHDRAWAL FROM THE STUDY

A participant may withdraw from the study at any time at his or her own request, or may be withdrawn at any time at the discretion of the investigator for safety, behavioral, compliance, or administrative reasons. The participant will then be permanently discontinued both from the study treatment and from the study at that time. Participants who withdraw from the study will not be replaced.

The primary reason for study treatment discontinuation should be documented on the appropriate eCRF.

If a participant withdraws consent from the study, the Sponsor may retain and continue to use any data collected before withdrawal of consent. Samples collected prior to withdrawal may be analyzed, unless the participant specifically requests that the samples be destroyed (as documented in the source documents) or local laws require destruction of the samples. However, if samples have been tested prior to withdrawal, results from those tests will remain as part of the overall research data.

All participants who discontinue from the study early will be asked to **return 2 weeks after the final dose of study drug** to complete the early termination visit and **17 weeks**

after the final dose of study drug for the safety follow-up visit. If participants dosed at home discontinue the study early, any remaining study drug doses should be returned to the study site (if applicable).

Every effort should be made to obtain a reason for participant discontinuation from the study. The primary reason for discontinuation from the study should be documented on the appropriate eCRF. However, participants will not be followed for any reason after consent has been withdrawn. If a participant requests to be withdrawn from the study, this request must be documented in the source documents and signed by the investigator.

Reasons for participant discontinuation from the study may include, but are not limited to, the following:

- Participant withdrawal of consent
- Study termination or site closure
- Any medical condition that the investigator or Sponsor determines may jeopardize the participant's safety if he or she continues in the study
- Investigator or Sponsor determines it is in the best interest of the participant

Participant non-compliance with the study and/or study procedures, defined as missing more than 3 consecutive dose administrations (with Q4W dosing regimen), more than 6 consecutive dose administrations (with Q2W dosing regimen), or > 12 consecutive dose administrations (with Q1W dosing regimen) because of non-safety related reasons or more than half of the dosing visits in a calendar year. See the schedule of activities in Section 1.3 for details on Early Termination and Safety Follow-up visits to be performed for participants who permanently discontinue study treatment. If a participant requests to be withdrawn from treatment or follow-up assessments, this request must be documented in the source documents and signed by the investigator.

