6.5 DOSE MODIFICATION

Rules regarding dose interruptions or modifications in participants who develop ARIA events are provided in Section A3-1. Discontinuation from study treatment is detailed in Section 7.1. Participant non-compliance and other potential reasons to discontinue a participant from the study are detailed under Section 7.2.

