- Psychedelic drugs and substances (e.g., psilocybin, LSD), recreational cannabis and illicit use of opioids (e.g., opium, morphine, fentanyl or diacetylmorphine/heroin) or ketamine are exclusionary at screening and during the entire study
- Nootropics and stimulant medications (e.g., piracetam, amphetamine, methylphenidate preparations, or modafinil) are exclusionary within 1 month of screening and throughout the study
- Any previous treatment with cholinesterase inhibitors (e.g., donepezil, galantamine, rivastigmine) and *N*-methyl-D-aspartate receptor antagonists (e.g., memantine) are exclusionary at screening. Cholinesterase inhibitors (e.g., donepezil, galantamine, rivastigmine) and *N*-methyl-D-aspartate receptor antagonists (e.g., memantine) are prohibited during the study unless the participant has progressed to dementia as determined by the iCAC

7. **DISCONTINUATION OF STUDY TREATMENT AND PARTICIPANT DISCONTINUATION OR WITHDRAWAL**

Study and site closure is described in [Appendix 1](#).

7.1 **DISCONTINUATION OF STUDY TREATMENT**

It may be necessary for a participant to permanently discontinue (definitive discontinuation) study treatment. If study treatment is definitively discontinued, the participant will remain in the study for additional assessments. See the schedule of activities (see Section 1.3) for data to be collected at the time of discontinuation of study treatment and for any further follow-up evaluations that need to be completed.

Participants must permanently discontinue study treatment if any of the following criteria are met:

- Any medical condition that the investigator determines (including upon the Sponsor's recommendation) may jeopardize the participant's safety if he or she continues to receive study treatment
- Investigator determination (including upon the Sponsor's recommendation) that treatment discontinuation is in the best interest of the participant
- Pregnancy
- Upon evidence of disseminated leptomeningeal hemosiderosis
- Upon evidence of intracerebral macrobleed

If study treatment is discontinued permanently for participants dosed at home, any remaining study drug doses should be returned to the study site (if applicable).

The primary reason for study treatment discontinuation should be documented on the appropriate eCRF.

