Participants who discontinue from the study treatment for any reason should be encouraged to continue with all remaining assessments until the end of the study. However, participants who are unwilling to return to the clinic will be asked to complete the Early Termination and safety follow-up visits within 2 weeks and 17 weeks, respectively from the final dose of study drug.

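### Section 7.2 lets missed doses end study participation at the investigator's discretion, so some Year 4 PACC-5 values needed under treatment policy may never be requested

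*Combined protocol and SAP*

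**What the plan says.** Section 7.1 covers stopping treatment: "If study treatment is definitively discontinued, the participant will remain in the study for additional assessments". It adds: "Participants who discontinue from the study treatment for any reason should be encouraged to continue with all remaining assessments". The shortened exit is a fallback there: "participants who are unwilling to return to the clinic will be asked to complete the Early Termination and safety follow-up visits". Section 4.1.4 likewise asks for the scheduled visits, but only from those who stop drug and stay in the study.

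Section 7.2 covers leaving the study. A participant "may be withdrawn at any time at the discretion of the investigator for safety, behavioral, compliance, or administrative reasons". The consequence follows: "The participant will then be permanently discontinued both from the study treatment and from the study at that time". Non-compliance is then defined as missing more than 3 consecutive doses (Q4W), more than 6 (Q2W) or more than 12 (Q1W) "because of non-safety related reasons or more than half of the dosing visits in a calendar year". Section 6.5 reads this the same way: "Participant non-compliance and other potential reasons to discontinue a participant from the study are detailed under Section 7.2". Anyone leaving early is asked back 2 weeks after the last dose (Early Termination) and 17 weeks after it (safety follow-up).

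For the primary estimand (Section 9.4.2.1, Table 11), treatment policy applies to study drug or condition-related (SDCR) withdrawal from treatment and to interruptions for ARIA-E or safety. A hypothetical strategy applies to withdrawal that is not study drug or condition-related (NSDCR). Under Section 9.4.2.2, treatment policy uses whatever data are available, while the hypothetical strategy censors and imputes.

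**The concern.** The two sections give different answers for a participant who misses many doses. Section 7.1 would keep that person in follow-up. Section 7.2 allows the site to end follow-up because of the missed doses.

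Treatment policy needs the outcome after the intercurrent event, whatever happened to dosing. If a site uses the Section 7.2 option in an SDCR case, a last PACC-5 is scheduled at Early Termination but none at Year 4. The analysis can change how the gap is modelled, but it cannot recover an observation that was never made. The site also decides without knowing whether the later values will count, because Section 9.4.2.1 leaves the details of the SDCR/NSDCR classification to the SAP.

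A second uncertainty concerns safety holds. In the non-compliance definition, the restriction to non-safety reasons stands before the half-of-visits criterion and is not repeated for it. The protocol itself orders some interruptions. Table A3-1 holds drug for symptomatic ARIA-E, or for asymptomatic ARIA-E of Bioclinica severity 4 or 5. Section 6.8.3 interrupts drug during short-term anticoagulation and indicates that this need not end study participation. The primary comparison is to be made regardless of both, yet Section 7.2 does not clearly exempt them.

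**Working it through.** **1. The plan's own figure.** Inputs from Section 9.2: 600 per arm, 35% dropout at Year 4, control CV 1.99, 40% reduction in decline, two-sided 0.05. Scale the control mean change to 1, so SD = 1.99 (taken as equal in both arms) and the difference is 0.40.
- Completers per arm: 600 × (1 − 0.35) = 390.
- Standard error: 1.99 × √(2/390) = 0.1425.
- Power (normal approximation): Φ(0.40/0.1425 − 1.96) = Φ(0.847) = 80.1%, against at least 80% stated.
- Completers needed for 80%: 389 per arm; 389/0.65 rounds up to 599, against 600 planned.

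The sample size is sound on its own assumptions.

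**2. Whose Year 4 value is exposed.**

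| Reason for missed dosing | Strategy | Effect of a Section 7.2 withdrawal |
|---|---|---|
| NSDCR | Hypothetical | None: later data are censored and imputed |
| SDCR | Treatment policy | Year 4 PACC-5 needed but not requested |
| Long hold for ARIA-E or other safety reason | Treatment policy | Same, if such holds count toward the half-of-visits criterion |

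**3. When the consecutive-dose option opens (non-safety reasons only).** More than 3 at Q4W is 4 doses × 4 = 16 weeks. More than 6 at Q2W is 7 × 2 = 14 weeks. More than 12 at Q1W is 13 × 1 = 13 weeks.

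**4. When the half-of-visits option opens.** Dose weeks come from Tables 1 and 2 (Q1W, 186 doses) and Tables 4 and 5 (Q2W, 96 doses). The threshold depends on where the calendar year falls, so the position of the year is an assumption in each row.

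| Study weeks in the calendar year | Regimen | Doses due | More than half | Shortest unbroken run |
|---|---|---|---|---|
| 1–52 | Q2W | 10 + 7 = 17 | 9 | Weeks 33–51, 20 weeks to next dose |
| 1–52 | Q1W | 13 + 15 = 28 | 15 | Weeks 37–51, 15 weeks |
| 53–104 | Q2W | 26 | 14 | 14 × 2 = 28 weeks |
| 53–104 | Q1W | 52 | 27 | 27 × 1 = 27 weeks |
| 1–26 only | either | 7 | 4 | – |

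This criterion does not require consecutive misses, so separate holds within one year can add up.

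**5. What cannot be computed.** No document gives a rate of withdrawal for missed doses, a split by arm, or a duration for ARIA-E or anticoagulation holds. Steps 3 and 4 show when the option becomes available, not how often it would be used.

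**The case against.** The case against is substantial, and much of it stands.

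- Retention is already the default in Section 7.1, and Section 7.2 is discretionary. A reader might infer that missed doses force withdrawal. The text does not say so: it creates an option, and the loss depends on site behaviour.
- The exposed group is narrow. The consecutive-dose criterion covers non-safety reasons only, and many such cases could be classed NSDCR. How many would be SDCR cannot be known, because the classification is left to the SAP, whose text is not in the documents reviewed.
- A reader might infer that every ARIA-E leads to a hold. It does not: asymptomatic severity 1 to 3 continues on drug. A hold ordered by the protocol is also not naturally read as non-compliance, anticoagulation is described as short-term, and the full-year thresholds need runs of 15 to 28 weeks. The wording still leaves the half-of-visits criterion open, which is enough to ask for clarification.
- Section 7.2 also refers to "Early Termination and Safety Follow-up visits to be performed for participants who permanently discontinue study treatment". This might be read as sending every treatment stopper out of follow-up. In context it is only a cross-reference to the schedule, and Section 7.1 says the opposite.
- The longitudinal model would use the earlier PACC-5 values and the Early Termination value. That limits the loss of information but does not supply the Year 4 outcome after treatment has stopped.

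**Conclusion.** The conflict between Sections 7.1 and 7.2 is real and touches the primary endpoint, but its reach is modest. It matters only if a site uses its discretion, and only for SDCR cases or for long safety interruptions if the half-of-visits criterion is read to include them. The number of Year 4 values lost, and the size and direction of any bias, cannot be derived.

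Two stronger conclusions are not supported. One is that the trial is underpowered: 35% dropout is already assumed, and nothing says that withdrawals for missed doses come on top of it. The other is that losses would fall mainly on the active arm and favour the drug: the documents give ARIA-E frequencies from earlier studies, but not the frequency or length of holds, nor how often sites would then withdraw participants.

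This is a cheap improvement of modest severity.

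**What to change.** In Section 7.2, state that missed doses alone do not end study participation, and that such participants are asked to continue the scheduled efficacy visits to Week 211, as Section 7.1 foresees. Align the compliance ground in the opening sentence of Section 7.2 and the cross-reference in Section 6.5; otherwise the same route stays open. Leave the other withdrawal grounds and loss to follow-up (Section 7.3) as they are.

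State whether the restriction to non-safety reasons also governs the half-of-visits criterion, and reconcile the answer with Sections 6.8.3 and 9.4.2.1.

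Section 7.2 now ends treatment and study together, and non-compliance is not among the mandatory treatment-stopping criteria in Section 7.1. The sponsor must therefore also reconcile the two sections on the treatment status of a participant who exceeds the missed-dose threshold. No dosing or treatment-stopping rule is proposed here.

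The cost is wording in Sections 7.2 and 6.5, a few more off-treatment efficacy visits, and a treatment effect estimate that may be less favourable because more off-treatment values enter it.

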7.3 PARTICIPANTS LOST TO FOLLOW-UP

A participant will be considered lost to follow-up if he or she repeatedly fails to return for scheduled visits and is unable to be contacted by the study site.

The following actions must be taken if a participant fails to return to the clinic for a required study visit:

- The site must attempt to contact the participant and reschedule the missed visit as soon as possible and counsel the participant on the importance of maintaining the assigned visit schedule. If the participant is unable or unwilling to comply with study visits, site personnel should assess reasons the participant is unable or unwilling to return to the clinic, and determine if there are ways to support participant participation.
- Before a participant is deemed lost to follow-up, the investigator or designee must make every effort to regain contact with the participant (where possible, 3 telephone

calls and, if necessary, a certified letter to the participant's last known mailing address or local equivalent methods). These contact attempts should be documented in the participant's medical record.

- Should the participant continue to be unreachable, he or she will be considered lost to follow-up and will be withdrawn from the study

8. STUDY ASSESSMENTS AND PROCEDURES

Written informed consent for participation in the study must be obtained from all participants and their study partners (non-professional caregivers) before performing any study-related procedures. Informed Consent Forms for enrolled participants, their study partners, and postdose observers, as well as for those who are not subsequently enrolled, will be maintained at the study site. Written informed consent for participation in the study must be obtained from:

- All participants before performing any study-related procedures (including optional prescreening evaluations)
- All study partners (non-professional caregivers) before performing any study-related screening procedures excluding the optional prescreen
- Each postdose observer before they undertake any study-related procedure, including any training

Informed Consent Forms for enrolled participants, their study partners, and postdose observers, as well as for those who are not subsequently enrolled, will be maintained at the study site.

Study procedures and their timing are summarized in the schedule of activities (see Section 1.3). Prospective approval of protocol deviations, also known as protocol waivers or exemptions, is not permitted.

Urgent safety concerns should be discussed with the Sponsor immediately upon occurrence or awareness to determine if the participant should continue or discontinue study treatment. Adherence to the study design requirements, including those specified in the schedule of activities, is essential and required for study conduct.

All screening evaluations must be completed and reviewed to confirm that potential participants meet all eligibility criteria before enrollment. The investigator will maintain a detailed record of all participants screened, to document eligibility or record reasons for screening failure, as applicable.

Medical history and baseline conditions, including clinically significant diseases, surgeries, cancer history (including prior cancer therapies and procedures), reproductive status, and use of alcohol and drugs of abuse will be recorded at baseline. Any medication or vaccine (including over-the-counter or prescription medicines, vitamins, herbal and homeopathic remedies, and nutritional supplements) used by the

participant within 3 months prior to the screening visit will be recorded at baseline. Demographic data, including age, sex, and self-reported race or ethnicity, relationship status of participants and their study partner, living situation and length of acquaintance will also be recorded and updated upon changes. At the time of each follow-up physical examination, an interval medical history should be obtained and any changes in medications, demographic data and allergies should be recorded.

As this study is being conducted in multiple geographic regions, it is likely that participants of different ethnic origins will be enrolled in the study. Although there is currently no indication that gantenerumab is metabolized or eliminated differently or that the treatment effect would be different in participants of different ethnic origins, collecting this information is essential to adequately evaluate the results of this study (e.g., possible differences in PK exposure [concentration of the drug in the blood] or treatment effect).

Participants will be closely monitored for safety throughout the study. Participants should be assessed for toxicity prior to each dose; treatment will be administered only if the clinical assessment and local laboratory test values are acceptable. Urgent safety concerns should be discussed with the Sponsor immediately upon occurrence or awareness to determine if the participant should continue or discontinue study treatment.

At applicable sites, certain study assessments may be performed by a MN professional at the participant's home or another suitable location to improve access and convenience for participants participating in the study. The Sponsor will select a healthcare company that will be responsible for providing MN services for home administration at participating sites (the MN vendor). The MN vendor is responsible for ensuring that all MN professionals are licensed, qualified, and in good standing, as per applicable regulations, and that appropriate background checks have been performed. If the investigator at a participating site determines that MN services are appropriate for a participant and the participant gives written informed consent to participate in MN visits, the MN network will communicate with the participant and the participant's site. Mobile nursing visits will be scheduled on specified visit days, to allow for relevant assessments to be performed by the MN professional. The MN Manual will specify the assessments that may be performed by a MN professional.

8.1 EFFICACY ASSESSMENTS

8.1.1 Clinical Outcome Assessments

Clinical outcome assessments (COAs) will be completed to assess the treatment benefit of gantenerumab as outlined in the schedule of activities (see Section 1.3) and in the order specified in Section 8.10. Cognitive, functional, neuropsychiatric and quality of life assessments (i.e., PACC-5, CDR, CF1a, Amsterdam Instrumental Activities of Daily Living Questionnaire Short Version [A-IADL-Q-SV], AD-CGI-S, AD-PGI-S, AD-SPGI-S,

GDS-30, and the EQ-5D-5L) will be administered. Detailed descriptions of COAs included in Study WN42444 are provided in Section 8.10.2.

8.1.2 Pharmacodynamic Assessments

Biomarker efficacy assessments are detailed in Section 8.5.

8.2 SAFETY ASSESSMENTS

8.2.1 Physical Examinations

A complete physical examination will include, at a minimum, assessments of the head, eyes, ears, nose, and throat, and the cardiovascular, dermatological, musculoskeletal, respiratory, gastrointestinal, genitourinary (optional), and neurological systems.

Any abnormality identified at baseline should be recorded on the General Medical History and Baseline Conditions eCRF.

A limited physical examination will be symptom-directed. Investigators should pay special attention to clinical signs related to previous serious illnesses. Changes from baseline abnormalities should be recorded in participant notes. New or worsened clinically significant abnormalities should be recorded as adverse events on the Adverse Event eCRF.

The schedule of activities (see Section 1.3) indicates when complete and limited physical examinations are to be recorded. During unscheduled visits, the investigator or designee may choose the appropriate scope of physical examination (complete vs. limited physical examination) depending on the reason for the unscheduled visit.

8.2.2 Vital Signs

Vital signs will consist of pulse rate and systolic and diastolic blood pressure measurements.

Blood pressure and pulse measurements will be assessed with a completely automated device. Manual techniques will be used only if an automated device is not available. If obtained manually, the pulse rate will be determined by radial pulse and should be counted for a minimum of 20 seconds.

Blood pressure and pulse measurements should be taken before blood collection for laboratory tests and preceded by at least 5 minutes of rest for the participant in a quiet setting without distractions (e.g., television, cell phones). The same arm should be used for all blood pressure measurements.

Record abnormalities observed at baseline on the General Medical History and Baseline Conditions eCRF. At subsequent visits, record new or worsened clinically significant abnormalities on the Adverse Event eCRF.

The schedule of activities (see Section 1.3) indicates when vital signs (pulse and blood pressure measurements) are to be recorded.

